DATA COLLECTION	Data will be collected prospectively on the number of catheters being used during the control and intervention periods.
STATISTICAL ANALYSES	
Objective 1
 
Data analysis will be performed using the generalised estimating equations, with the duration of catheterisation as the dependent variable, and intervention as the independent variable.
 
Objective 2
 
Through an online survey and focus group the data analysis process will aim to investigate pre-determined themes reflected in the study's objectives as well as to identify emerging themes.

DISSEMINATION	The investigators will implement a dissemination plan that will include communication strategies for all stakeholders, a publication plan (to minimally include a protocol paper and primary outcomes papers) and presentations at national and international conferences.

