### ***Confounders***

Potential confounders include the different staff inserting and caring for patients with an indwelling catheter and the indications for urinary catheterisation. The cluster randomised design of this study minimises many of these issues, as wards (clusters) act as their own control. Further, there is no reason to suggest a fundamental change in the control and intervention periods for these variables. Duration of the intervention might have a confounding effect on the outcome variables and will be accounted for in data analysis.

Clinical staff working on a casual basis or across wards have the potential to provide responses to the survey or focus group from a range of perspectives, based on their experiences on different wards. To minimise this, the survey will focus the respondent to experiences in one particular area and obtain details about their exposure to working in different wards/hospital units.

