### ***Data analysis***

*Objective 1: To determine the efficacy of an electronic reminder system in reducing urinary catheter usage.*

The primary outcome measure is the duration of catheterisation, and the study aims to evaluate the effect of the intervention. The analysis will be performed using the generalised estimating equations, using the duration of catheterisation as the dependent variable and intervention as the independent variable. Duration of the intervention will be treated as a confounding variable. It is anticipated that duration of catheterisation will be normally distributed, but exploratory analyses (and where necessary transformation) will be performed. Robust standard errors will be used to adjust for correlation at ward level and autocorrelation in time. There is no expected delay in the effect of the intervention on the outcome.

*Objective 2: To determine whether the CATH TAG has an effect on nurses' ability to deliver patient care.*

Survey:

Data from the anonymous online survey will be analysed using SPSS. It is anticipated that data will be normally distributed but exploratory analyses will be performed, including testing of assumptions of linearity, homoscedasticity, multicollinearity and normality of errors and if necessary transformation of data. Validity and reliability will be examined. Subsequently a general satisfaction score and individual satisfaction scores for the four dimensions of nurses' experiences with the CATH TAG (Ease of use, Effectiveness, Changes in ownership, Barriers) will be calculated. Regression analysis will be conducted to determine if the duration of the intervention or the ward nurses primarily work on had an effect on nurses' experiences with the CATH TAG.

Any problems reported in the open questions will be taken into the focus group to be discussed and subsequently analysed qualitatively (see below).

Focus group:

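### The primary stepped-wedge model has no calendar-period term and adjusts only for an undefined duration of the intervention, so any secular trend biases the effect estimate

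*Protocol*

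**What the plan says.** Protocol, Data analysis (Objective 1), specifies generalised estimating equations "using the duration of catheterisation as the dependent variable and intervention as the independent variable". One adjustment variable is named: "Duration of the intervention will be treated as a confounding variable". The Confounders section repeats it: "Duration of the intervention might have a confounding effect on the outcome variables and will be accounted for in data analysis". The Synopsis gives the model "with the duration of catheterisation as the dependent variable, and intervention as the independent variable", with no time term.

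Time is otherwise mentioned only for the variance: "Robust standard errors will be used to adjust for correlation at ward level and autocorrelation in time".

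The covariate is not defined. The best guide is the survey analysis in the same section: "Regression analysis will be conducted to determine if the duration of the intervention or the ward nurses primarily work on had an effect". That survey is run once, in month 6, so calendar time is the same for every respondent. Duration can differ between nurses only as time since their ward crossed over.

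Study design and Figure 1 give the rollout: ten wards, two crossing over every four weeks, six months, with all wards on control in month 1 and all on intervention in month 6.

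**The concern.** In a stepped wedge, intervention status is tied to calendar time by construction. Randomising the order of crossover makes a comparison between wards within the same month valid, but the model uses only that comparison if it contains period effects. Without them it draws largely on before-versus-after contrasts within wards, and these carry any trend in catheter practice.

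Time since crossover is a poor substitute. It is a feature of the exposure and does not vary among control ward-months, so it cannot describe a trend during the control phase. It absorbs part of a drift and leaves the rest in the intervention coefficient.

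This is the primary efficacy analysis of an unblinded, single-hospital trial. A trend from season, staffing or general attention to catheters could create an apparent benefit or hide a real one. The protocol itself names the model and its only covariate, so this is not a detail left open for an analysis plan.

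**Working it through.** **Inputs.** From Sample size: 10 wards, 35 catheterised patients per ward-month (35 × 10 × 6 = 2100), ICC 0.1, 50% v 40% in situ on day 4, alpha 0.05, power 81%. From Figure 1: 6 periods and 5 steps. Assumed: a two-sided test, a normal approximation, and the average binomial variance (0.25 + 0.24)/2 = 0.245.

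**1. The plan's own power figure.** The Hussey-Hughes variance has fixed period effects and a random ward effect:

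Var = I·s²(s² + T·τ²) / [(I·U − W)s² + (U² + I·T·U − T·W − I·V)τ²]

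- I = 10, T = 6, s² = 0.245 × 0.9/35 = 0.0063, τ² = 0.245 × 0.1 = 0.0245.
- U = 30 intervention ward-months; W = 0 + 4 + 16 + 36 + 64 + 100 = 220; V = 2 × (25 + 16 + 9 + 4 + 1) = 110.
- Numerator: 10 × 0.0063 × (0.0063 + 0.147) = 0.00966.
- Denominator: 80 × 0.0063 + 280 × 0.0245 = 7.364.
- Var = 0.001312, SE = 0.0362. Power = Φ(0.10/0.0362 − 1.96) = Φ(0.80) = 78.9%, or 79.7% with the variance taken at 40%.

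Generalised least squares with the same variances and intervention only gives SE 0.0231 and power Φ(0.10/0.0231 − 1.96) = 99.1%.

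**2. Imbalance in calendar time.**
- Intervention ward-months: mean month (2×1 + 3×2 + 4×3 + 5×4 + 6×5)/15 = 4.67.
- Control ward-months: (1×5 + 2×4 + 3×3 + 4×2 + 5×1)/15 = 2.33.
- The correlation of intervention with month is 0.68.
- A ward treated for its last k months has mean treated month (13 − k)/2 and mean control month (7 − k)/2. The difference is 3.0 months for every ward.

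**3. False effect per 1 percentage point of drift per month.** This is the exact projection of a linear trend on each model, with no true effect.

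| Mean model | Exchangeable, ICC 0.1 | Independence |
|---|---|---|
| Intervention only | 3.0 | 2.3 |
| Intervention + duration, counted from 0 | 2.1 | 1.7 |
| Intervention + duration, counted from 1 | 1.2 | 1.2 |
| Intervention + period effects | 0 | 0 |

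The protocol states neither the coding nor the working correlation, so the stated model spans 1.2 to 2.1 points.

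**4. False-positive rate** (2000 simulations each; exchangeable; duration counted from 0). A drift of 0.02 SD per month is about 1 point, since 0.02 × √0.245 = 0.0099.

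| Model and drift | Model-based SE | Robust SE |
|---|---|---|
| Stated model, no drift | 5.0% | 9.9% |
| Stated model, 0.02 SD/month | 12.0% | 19.5% |
| Period effects, no drift | 4.7% | 11.6% |
| Period effects, 0.02 SD/month | 5.1% | 12.1% |

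The no-drift rows show that robust standard errors with 10 wards already reject about 10 to 12% of the time. Only the rise above that baseline is due to drift.

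**5. An effect that grows with exposure.** Suppose no drift and an effect of −5 points at crossover that grows by 3.75 points a month. Mean exposure over intervention ward-months, counted from 0, is 1.33 months, so the average effect is −5 − 3.75 × 1.33 = −10.
- Stated model, duration from 0: coefficient −5.0.
- Period effects with a single indicator: −3.4.
- Period effects plus linear time since crossover: −5.0 and −3.75 per month, which average to −10.

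**The case against.** Several replies deserve an answer.

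- **Wards are their own controls, and robust errors handle time.** Own-control comparison removes stable differences between wards; it does not remove a trend. Robust errors change the variance, not the mean.
- **No change is expected.** The Confounders section says "there is no reason to suggest a fundamental change in the control and intervention periods for these variables", but this refers to inserting and caring staff and to indications, and is asserted. By Table 4, data collection runs from December to May. The size and direction of any trend remain unknown, and without a trend there is no bias from this source. That part of the objection stands.
- **Duration may have meant study time.** The term is undefined, so this is possible, though the survey wording points the other way. If it was meant, the text still needs correcting.

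Three stronger readings are not supported.

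- A reader might infer that the intervention coefficient is simply the effect at zero exposure. That requires duration to enter linearly, counted from 0, which is not stated. It matters only if the effect changes with exposure, and the protocol says "There is no expected delay in the effect of the intervention on the outcome". With a constant effect and no drift, the coefficient is right.
- A reader might infer that 81% power proves the calculation contained period effects. It rules out an intervention-only model, but the stated model with duration counted from 1 gives about 83% (SE 0.0343), so the figure alone does not settle it. Counted from 0, it gives about 97%.
- A reader might take the whole excess false-positive rate as due to the missing term. About half of the 19.5% is present without drift.

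**Conclusion.** The point holds: the primary model as written leaves intervention confounded with calendar time, and nothing elsewhere in the protocol repairs it. For each percentage point of monthly drift, 1.2 to 2.1 points of false effect remain under the stated model, or 12 to 21% of the 10-point target. Period effects remove it.

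The drift is an assumption; one point a month means five points from month 1 to month 6, and the bias may go either way. The figures use a linear trend and the day-4 in-situ probability from the sample-size section, whereas the analysis models duration of catheterisation. They therefore illustrate the bias and do not predict its size on the analysis scale.

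**What to change.** In Data analysis (Objective 1), state that the primary GEE includes categorical effects for the six 4-week periods and one intervention indicator, whose coefficient is the primary effect. Remove duration of the intervention as a confounder there and in Confounders, and align the Synopsis. Specify a small-sample correction for the robust standard errors with 10 wards, since period effects alone leave the test rejecting about 12% under the null.

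Examine time since crossover in a secondary model that keeps the period effects, defines the coding, and reports the effect averaged over exposure time. This is needed because a single indicator with period effects can misstate a growing effect even more than the stated model does (−3.4 v −5.0 for a true average of −10).

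The cost is wording and a wider standard error, about 0.036 against 0.023 for intervention only. The power calculation already implies roughly that width: 79% recomputed against 81% stated. The small-sample correction will take some further power, which the normal-approximation figures above do not include.

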### ***Study design***

A stepped wedge cluster randomised controlled study will be undertaken in one hospital over a 24-week period (Figure 1). A mixed methods approach will be used, as the study includes a qualitative approach. The clusters in the study are pairs of individual hospital wards. The stepped wedge design includes an initial period where no wards are exposed to the intervention. Afterwards, at regular intervals (the "steps") two wards, forming one cluster, are randomised to cross over from the control to the intervention with the process continuing until all enrolled wards have crossed over. There will be a random sequential allocation of the intervention to the wards, i.e. each enrolled ward will be introduced to the intervention two at a time, approximately every 4 weeks until week 20, when all wards would have been exposed to the intervention. The study design enables each ward to act as its own control, which removes the potential for some confounders such as variations in ward size and case mix. Staggered commencement and duration of the intervention, supports feasibility while maintaining the rigour of the study. This design will allow research staff to work with individual wards as they change over, maximising consistency of the intervention and aiding implementation. In addition, data collection continues throughout the study, so that each cluster contributes observations under both control and intervention observation periods. In month 6 of the study, an online survey of nursing staff will be administered. Approximately two months after the stepped wedge study is completed, a focus group will be conducted.

Ward	1 month	2 months	3 months	4 months	5 months	6 months	Post study (2 months)
A + B	Blue (horizontal lines)	Green (vertical lines)	Green (vertical lines)	Green (vertical lines)	Green (vertical lines)	Green (vertical lines)	Survey  Focus group
C + D	Blue (horizontal lines)	Blue (horizontal lines)	Green (vertical lines)	Green (vertical lines)	Green (vertical lines)	Green (vertical lines)	
E + F	Blue (horizontal lines)	Blue (horizontal lines)	Blue (horizontal lines)	Green (vertical lines)	Green (vertical lines)	Green (vertical lines)	
G + H	Blue (horizontal lines)	Blue (horizontal lines)	Blue (horizontal lines)	Blue (horizontal lines)	Green (vertical lines)	Green (vertical lines)	

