#### Sample size:

The at risk population has been defined as patients receiving catheters in hospital. Based on pilot work, an estimated 25% of admissions will receive a catheter. We estimate that, at baseline, the median duration of catheterisation is 4 days (equivalent to a 50% probability that a catheter will be in situ on day 4). We aim to detect a difference of 20% relative risk (10% absolute risk) reduction in catheterisation on day 4, using a stepped wedge study. It is assumed the intra-ward correlation in catheter duration is  $\rho=0.1$ ). Based on pilot work it is anticipated that there will be 50 patients with a catheter per month on each ward and the study will continue for 6 months.

A power calculation was performed using the stepped wedge module in Stata. This accounts for both the clustering in outcomes by ward, as well as the paired/crossover design of the study.

At a significance level of 0.05, 2100 patients (10 wards, with 2 wards implementing the intervention at each month, forming one cluster) will be required to demonstrate a change in the probability of a catheter being in situ on day 4 from 50% to 40% with a power of 81%. Similar power would be expected with 35 patients with catheters per month in 10 wards, with two wards implementing the intervention each month (n=2100, power 81%).

*Objective 2: To determine whether the CATH TAG has an effect on nurses' ability to deliver patient care.*

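### Robust standard errors are specified for about ten wards with no small-sample correction and no single cluster unit, so the 0.05 level is not secured

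*Protocol*

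**What the plan says.** The Data analysis section for Objective 1 fits generalised estimating equations (GEE) with catheter duration as the outcome, the intervention as the explanatory variable and length of exposure to it as a confounder. On variance it says: "Robust standard errors will be used to adjust for correlation at ward level and autocorrelation in time". It gives no finite-sample correction, reference distribution (normal or t), working correlation or calendar-time term. The Sample size section sets the significance level at 0.05.

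The cluster is described in two ways.

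- **Pair (5 clusters).** Study design: "The clusters in the study are pairs of individual hospital wards". Sample size: "with 2 wards implementing the intervention at each month, forming one cluster".
- **Ward (10 clusters).** Confounders: "as wards (clusters) act as their own control". Data analysis puts the correlation at ward level. Sample size itself says "It is assumed the intra-ward correlation in catheter duration is" 0.1 and describes its calculation as allowing for clustering by ward. Randomisation and blinding speaks of assigning wards.

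Ten wards is a planning figure. The section on areas of the hospital gives it as a minimum.

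**The concern.** The GEE sandwich variance is justified by a large number of independent clusters. With few, it is biased downwards because fitted residuals are smaller than true errors. It is also noisy, so a normal critical value is too small. Ten clusters is few and five is very few. The nominal 0.05 would then not be the real level of the confirmatory test, and confidence intervals would be too narrow.

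The cluster contradiction adds to this. Whether there are 5 or 10 independent units determines the size of the problem, the degrees of freedom and the set of crossover orders the randomisation could have produced. An analyst cannot settle that from the text.

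**Working it through.** **1. The plan's own figure.** Inputs from Sample size: 50% versus 40% in situ on day 4, correlation 0.1, two-sided 0.05 (sidedness assumed). "Similar power would be expected with 35 patients with catheters per month in 10 wards" gives 10 × 6 × 35 = 2,100 patients. The Hussey-Hughes variance for I wards and T periods, with s² = within-ward variance / 35 and between-ward variance τ², is

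Var = I·s²(s² + Tτ²) / [(IU − W)s² + (U² + ITU − TW − IV)τ²]

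For the layout in Figure 1, I = 10, T = 6, U = 30, W = 220, V = 110. Take total variance 0.245 (mean of 0.25 and 0.24), so τ² = 0.0245 and s² = 0.2205/35 = 0.0063. Then Var = 0.001312, SE = 0.0362, and power = Φ(0.10/0.0362 − 1.96) = 78.9%. Using 0.25 or 0.24 as total variance gives 78.0% or 79.7%. The stated 81% is thus approximately reproduced.

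Five pairs of 70 patients per month give 77.5-79.1% on the same basis. The stated power therefore cannot show which unit was used.

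**2. Type I error of the robust test.** The layout of step 1 was simulated with no effect and no secular trend, 20,000-40,000 runs per setting. At a true rate of 10%, the Monte Carlo standard error with 20,000 runs is √(0.1 × 0.9/20,000) = 0.2 points. For cluster i with design matrix Zᵢ, working weight W and residual rᵢ,

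V = A⁻¹ (Σ Zᵢ′W rᵢrᵢ′W Zᵢ) A⁻¹, A = Σ Zᵢ′W Zᵢ

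and the null is rejected when |β̂|/√V > 1.96. Assumptions: equal cell sizes, correlation 0.05 or 0.1, cluster autocorrelation 0.8 or 1, independence or exchangeable working correlation.

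| Model | 10 wards | 5 pairs |
|---|---|---|
| Stated: intervention + length of exposure | 9.1-10.3% | 14.3-17.0% |
| Intervention only | 9.7-10.8% | 15.8-19.5% |
| Calendar-time terms added | 9.8-14.8% | 16.1-27.5% |

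Fitting the stated model by GEE to patient-level data (1,000 runs per setting, normal and right-skewed durations) gave 8.8-12.9% and 14.8-16.4%. Using 50 patients per ward-month barely changed the results.

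**3. With corrections.**

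| Method | 10 wards | 5 pairs |
|---|---|---|
| Kauermann-Carroll, t on M − 2 df, all models | 3.6-6.4% | 1.6-5.4% |
| M/(M − 1) scaling, t on M − 1 df, stated model | about 5% | 4-6% |
| M/(M − 1) scaling, t on M − 1 df, all models | 4.6-8.5% | 4.1-11.7% |

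Here M is the number of clusters. Kauermann-Carroll replaces rᵢ by (I − Hᵢ)^(−1/2) rᵢ, with Hᵢ = Zᵢ A⁻¹ Zᵢ′W.

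**4. Consequence of the unit.** Degrees of freedom on M − 2 are 8 for wards and 3 for pairs. The possible crossover orders number 10!/2⁵ = 113,400 if wards are drawn two per step, and 5! = 120 if fixed pairs are drawn.

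**The case against.** The strongest reply is that the protocol does not say the variance is uncorrected or the reference normal. It is silent on both, and an analysis plan that is not shown may settle them. This matters numerically: simple M/(M − 1) scaling with a t reference already brings the stated model close to 5%. That part stands, so the inflated rates are conditional. What remains is that the protocol does choose a variance method, and the method as named, in its ordinary form, does not hold the level at this number of clusters.

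A reader might infer that the trial's error rate could be as high as 28%. The documents do not support that. The 27.5% figure needs five pairs as clusters, calendar-period terms without the exposure-length term, and an independence working correlation, all together. The Data analysis section states none of these and places the correlation at ward level.

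Nor do the documents show that five pairs are the true unit of correlation. The pair label may only name the two wards that share a step, and the inputs to the power calculation are ward-level. Even so, the text needs reconciling, and an unseen analysis plan does not excuse a protocol that defines its cluster in two ways.

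**Conclusion.** The point holds in conditional form. With the ordinary sandwich variance and a normal reference, the nominal 5% test of the stated model runs at about 10% with 10 wards, twice nominal. If pairs are the clusters it runs at about 14-17%, roughly three times nominal. Adding calendar-time terms would give about 10-15% and 16-28%. These figures rest on the protocol's correlation of 0.1 (0.05 was also tried) and on assumed equal cell sizes, outcome distributions and autocorrelation. More than ten wards would reduce them.

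The contradiction over the cluster unit is plain in the text and needs no simulation. Both matters should be fixed, and both are matters of specification: neither calls the design or the data collection into question.

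**What to change.** 1. State one cluster unit and use it in randomisation, power and analysis: the ward, if wards are individually randomised two per step; the pair, if pairs are formed first and then randomised. Amend Study design, Confounders, Sample size and Data analysis to agree.
2. In Data analysis, specify small-sample-corrected robust standard errors (for example Kauermann-Carroll) referred to t with clusters minus 2 degrees of freedom. This gives about 4-6% with 10 wards. With 5 pairs it is somewhat conservative.

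A permutation test over the allowed crossover orders is a reasonable sensitivity analysis but is not needed to repair the level.

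The cost is a few sentences, wider intervals and some power. On 8 degrees of freedom the critical value rises from 1.96 to 2.31. With the noncentrality of step 1, 0.10/0.0362 = 2.76, a noncentral t calculation gives power of about 68% in place of 78.9% at 35 patients per ward-month. At the 50 per ward-month that the protocol anticipates, the same calculation gives about 82% in place of 91%. These are indicative only, since the power calculation concerns a day-4 proportion and the analysis concerns duration. Power should be restated under the method chosen.
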